5.2.5. Exploratory Endpoints

- 1. Change from baseline to Day 29 in expression of the COX-2, Cytokeratin 10, HLA-DR, IFN-γ, IL-1β, and IL-8 genes in the lid wiper.
- 2. Change from baseline to Day 29 in expression of the COX-2, Cytokeratin 10, HLA-DR, IFN-γ, IL-1β, and IL-8 genes in the bulbar conjunctiva.
- 3. Change from baseline to Day 29 in MMP-9 Activity in tears.
- 4. Change from baseline to Day 29 in Prostaglandin levels (PGE₂, PGD₂, PGF_{2x}, TxB₂, and PGI₂) in tears.
- 5. Pearson correlations between the response of 7-item questionnaire symptoms, corneal staining, conjunctival staining, lid wiper staining, TBUT, and biomarkers with baseline scores for tear osmolarity, Meibomian gland assessment, and the Schirmer test.

5.2.6. Exploratory Analyses

The expression of each gene and change from baseline in the lid wiper will be summarized separately by treatment and study visit. For each of the 6 genes, the change from baseline at Day 29 will be assessed for differences between the 0.017% P-321 treatment group and placebo using an ANCOVA model with fixed effects for treatment, study site, and baseline value.

The expression of the same 6 genes in the bulbar conjunctiva, MMP-9 activity levels, and prostaglandin levels will be analyzed in a similar manner. A secondary analysis will be performed assessing the change from baseline at Day 15 for MMP-9 and Prostaglandins.

CONFIDENTIAL Page 20 08 August 2017

The Pearson correlations between the change from baseline to Day 29 in corneal stain score with the baseline scores for tear osmolarity, Meibomian gland assessment, and the Schirmer test and their corresponding p-values will be presented by treatment group and overall.

The analysis will be repeated for each symptom from the 7-item, SANDE and SPEED questionnaires, corneal staining, conjunctival staining, lid wiper staining, TBUT, and biomarkers.

5.3. SAFETY

Safety analyses will be run separately on Safety population and the Run-in population.

5.3.1. Adverse Events

Adverse events will be mapped to a Medical Dictionary for Regulatory Activities (MedDRA) version 19.1 preferred term and system organ classification. If a subject experiences multiple events that map to a single preferred term, the greatest severity grade and strongest investigator assessment of relation to study medication will be assigned to the preferred term for the appropriate summaries. Should an event have a missing severity or relationship, it will be classified as having the highest severity and/or strongest relationship to study medication. Summaries of incidence rates (frequencies and percentages) of individual AEs by MedDRA system organ class and preferred term will be prepared. Such summaries will be displayed for all TEAEs, TEAEs by maximum severity, and TEAEs by strongest relationship to study drug. Serious AEs and AEs leading to discontinuation of study drug will also be summarized. Separate summaries will be performed for those AEs occurring during the placebo run-in period.

All adverse events reported will be listed for individual subjects showing both verbatim and preferred terms. AEs will be flagged by run-in or double-masked treatment period as appropriate.

Any adverse event with a missing onset date will be considered to be a TEAE occurring during the double-masked treatment period.

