3.3.5. Imputation of Incomplete Dates

An incomplete date is any date for which either the day, month or year is unknown, but all three fields are not unknown. An incomplete date occurs when the exact date an event occurred or ended cannot be obtained from a subject. For many of the analyses, a complete date is necessary in order to determine if the event should be included in the analysis (i.e., if the event is treatment-emergent) or to establish the duration of an event. In such cases, incomplete dates will be imputed.

For purposes of imputation, all events with an incomplete end date are assumed to have ended on or before the day the form was completed. In an effort to minimize bias, the project statistician will impute dates in a systematic, but reasonable manner. For missing dates during the placebo run-in phase, if the month/year is the same as the Day -14 month/year then the date will be set to the date of Day -14. In other cases, missing days will be imputed as the day component of Day -14; missing months/years will be imputed as the month/year of Day -14. For missing dates during the double-masked phase, if the month/year is the same as the Day 1 month/year then the date will be set to the date of Day 1. In other cases, missing days will be imputed as the day component of Day 1; missing months/years will be imputed as the month/year of Day 1. A list of incomplete and imputed dates will be prepared by the project statistician or statistical programmer(s) and will be submitted for review by the clinical project manager and sponsor.

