3.3.7. Definitions and Terminology

Baseline Value

For purposes of analysis, the baseline value is defined as the last non-missing value obtained prior to administration of the first dose of double-masked study drug.

Day 1

Day 1 is the day/time that the double-masked study drug is first initiated.

Study Day

Study Day is defined relative to Day 1.

For events occurring prior to Day 1, the study day is calculated as:

Study Day = event date - date of Day 1.

For events occurring after Day 1, the study day is calculated as:

Study Day = event date - date of Day 1 + 1.

Study Visit

Study Visit is the nominal visit as recorded on the CRF.

Change from Baseline

Change from baseline for a given endpoint is defined as the Study Day X value minus the Baseline Value.

Adverse Event (AE)

An adverse event is any untoward medical occurrence in a subject or clinical investigation subject administered a pharmaceutical product; which does not necessarily have a causal relationship with this treatment. All adverse events will be recorded on the Adverse Event CRF.

Treatment-emergent Adverse Event (TEAE) for Placebo Run-in Period

During the placebo run-in period, a treatment-emergent AE (TEAE) is an AE that either commenced following initiation of the placebo run-in period study treatment or was present prior to study treatment but increased in frequency or severity following initiation of study treatment.

Additionally, it is assumed that an AE which was reported to have started on Day -14 (start of placebo run-in period) without an associated onset time occurred after the initiation of study treatment and is therefore a treatment-emergent adverse event (TEAE).

Treatment-emergent Adverse Event for Double-masked Period

During the double-masked period, a treatment-emergent AE is an AE that either commenced following initiation of the double-masked period study treatment or was present prior to study treatment but increased in frequency or severity following initiation of double-masked study treatment. Additionally, it is assumed that an AE which was reported to have started on Day 1 (start of double-masked period) without an associated onset time occurred after the initiation of study treatment and is therefore a treatment-emergent adverse event. AEs reported without an onset date are also assumed to be TEAEs.

Treatment-related Adverse Event

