4.2. SAFETY POPULATION

The Safety Population will include all subjects who receive at least one dose of double-masked study medication in either eye. All safety analyses for the double-masked portion of the study will be conducted on the Safety Population, analyzed as treated.

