4.3. RUN-IN POPULATION

The Run-in Population will include all subjects who receive at least one dose of single-masked placebo in either eye during the run-in period. Safety analyses for the single-masked portion of the study will be conducted on the Run-in Population.

5. STATISTICAL METHODS

Descriptive statistical methods will be used to summarize the data from this study. Unless stated otherwise, the term "descriptive statistics" refers to number of subjects (n), mean, median, standard deviation (SD), minimum and maximum for continuous data and frequencies and percentages for categorical data. All data collected during the study will be included in data listings. Unless otherwise noted, the data will be sorted first by treatment group, subject number, and then by date within each subject number.

The term 'treatment group' refers to all subjects on the same dosing regimen. There will be 2 treatment groups in this study: 0.017% P-321 Ophthalmic Solution and placebo.

All statistical testing will be two-sided and will be performed using a significance (alpha) level of 0.05 unless otherwise stated.

The statistical analyses will be conducted with the SAS® System version 9.4 or higher. All analyses will be subject to formal verification procedures. Specifically, results will be verified utilizing

CONFIDENTIAL Page 14 08 August 2017

independent programming prior to issuance of the draft statistical report. All documents will be verified by the lead statistician to ensure accuracy and consistency of analyses.

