14.2.8.1	Summary of SANDE Part 2 Symptom Frequency Score
14 2 8 2	Summary of SANDE Part 2 Symptom Severity Score

14.2.9.1	Summary of SANDE Questionnaire Part 1 Symptom Frequency Score
14.2.9.2	Summary of SANDE Questionnaire Part 1 Symptom Severity Score
14.2.10.1	Proportion of Subjects with at Least a 20% Improvement from Baseline in the
	SANDE Part 1 Global Symptom Score
14.2.10.2	Proportion of Subjects with at Least a 20% Improvement from Baseline in the
	SANDE Part 1 Symptom Frequency Score
14.2.10.3	Proportion of Subjects with at Least a 20% Improvement from Baseline in the
	SANDE Part 1 Symptom Severity Score
14.2.11.1	Proportion of Subjects with at Least a 10% Improvement from Previous Visit in
	the SANDE Part 2 Symptom Frequency Score
14.2.11.2	Proportion of Subjects with at Least a 10% Improvement from Previous Visit in
	the SANDE Part 2 Symptom Severity Score
	3 1
Exploratory	(all analyses on mITT population)
14.2.12.1	Summary of Expression of the COX-2 Gene in the Lid Wiper
14.2.12.2	Summary of Expression of the Cytokeratin10 Gene in the Lid Wiper
14.2.12.3	Summary of Expression of the HLA-DR Gene in the Lid Wiper
14.2.12.4	Summary of Expression of the IFN-γ Gene in the Lid Wiper
14.2.12.5	Summary of Expression of the IL-1β Gene in the Lid Wiper
14.2.12.6	Summary of Expression of the IL-8 Gene in the Lid Wiper
14.2.13.1	Summary of Expression of the COX-2 Gene in the Bulbar Conjunctiva
14.2.13.2	Summary of Expression of the Cytokeratin 10 Gene in the Bulbar Conjunctiva
14.2.13.3	Summary of Expression of the HLA-DR Gene in the Bulbar Conjunctiva
14.2.13.4	Summary of Expression of the IFN-γ Gene in the Bulbar Conjunctiva
14.2.13.5	Summary of Expression of the IL-1β Gene in the Bulbar Conjunctiva
14.2.13.6	Summary of Expression of the IL-8 Gene in the Bulbar Conjunctiva
14.2.14	Summary of MMP-9 Activity in Tears
14.2.15	Summary of Prostaglandin Levels in Tears
14.2.16	Pearson Correlations Between Responses and Baseline scores for tear osmolarity,
	Meibomian gland assessment and the Schirmer test
Safety	
14.3.1.1.1	Summary of Treatment-emergent Adverse Events – Double Masked Period (Safety
	Population)
14.3.1.1.2	Summary of Treatment-emergent Adverse Events – Placebo Run-in Period (Run-in
	Population)
14.3.1.2.1	Treatment-emergent Adverse Events by System Organ Classification, Preferred
	Term, and Greatest Severity – Double Masked Period (Safety Population)
14.3.1.2.2	Treatment-emergent Adverse Events by System Organ Classification, Preferred

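### An adverse event with no onset date is always assigned to the double-masked period, so in a subject who took only run-in placebo it appears in no adverse event summary table

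*SAP*

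**What the plan says.** SAP 5.3.1 sets the rule: "Any adverse event with a missing onset date will be considered to be a TEAE occurring during the double-masked treatment period". SAP 3.3.7 has a companion sentence, "AEs reported without an onset date are also assumed to be TEAEs". It stands only in the paragraph defining treatment-emergent events for the double-masked period. The paragraph for the run-in period has no rule for a missing date.

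The two safety populations are defined by treatment received. For the double-masked part, SAP 4.2 says "The Safety Population will include all subjects who receive at least one dose of double-masked study medication in either eye". For the run-in part, SAP 4.3 says "The Run-in Population will include all subjects who receive at least one dose of single-masked placebo in either eye during the run-in period".

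The summaries are split by period as well as by population. SAP 5.3.1 adds: "Separate summaries will be performed for those AEs occurring during the placebo run-in period". In SAP Section 10, the title of Table 14.3.1.1.1 begins "Summary of Treatment-emergent Adverse Events – Double Masked Period (Safety" and that of Table 14.3.1.1.2 begins "Summary of Treatment-emergent Adverse Events – Placebo Run-in Period (Run-in". The other adverse event tables come in the same pairs.

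SAP 3.3.5 imputes dates, but only where at least one of day, month and year is known.

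**The concern.** Treating an undated event as treatment-emergent is normally the cautious choice, because it keeps the event in the tables. Here the rule also fixes the period, and it fixes the same period for everyone. For a subject with no double-masked dose, that period is one the subject never entered.

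The design expects such subjects. Everyone who passes screening takes placebo for about two weeks and must then meet the randomization criteria in Protocol 6.3. Protocol 10.1 requires adverse events to be recorded for all who receive run-in medication, and Protocol 16.3 asks for the reported events of those who enter the run-in but do not qualify for randomization. The Protocol Synopsis bases the safety analyses on subjects with at least one dose of study medication. An event that was collected in a dosed subject should therefore be counted in the table for the treatment that the subject received. As written, the rule can prevent this. What is at stake is the completeness of the run-in safety tables.

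**Working it through.** The plan gives no figure to reproduce on this point. The check follows an event through the rules.

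**Inputs**
- Period for a wholly missing onset date: double-masked, for any event (SAP 5.3.1; SAP 3.3.7).
- Double-masked tables: double-masked events in the Safety Population, which requires a double-masked dose (SAP 4.2; SAP 10).
- Run-in tables: run-in events in the Run-in Population (SAP 4.3, 5.3.1; SAP 10).
- Partly known dates: handled separately in SAP 3.3.5, so not at issue.
- Screened about 125, randomized about 65 (SAP 1.1).

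**Four cases, all in subjects who took run-in placebo**

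| Double-masked dose | Onset date | Period assigned | In run-in tables | In double-masked tables |
|---|---|---|---|---|
| No | Known, in run-in | Run-in | Yes | No |
| No | Wholly missing | Double-masked | No (period) | No (population) |
| Yes | Known, in run-in | Run-in | Yes | No |
| Yes | Wholly missing | Double-masked | No | Yes |

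Only the second case ends in no table. Two other parts of the SAP might seem to rescue it, and neither does. Table 14.3.1.5.2, on discontinuation in the run-in period, is labelled with the Safety Population, but it still requires a run-in event and its label excludes run-in-only subjects. The instruction in SAP 5.3.1 to flag events by period where appropriate does not set aside a rule that covers any event.

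**How many subjects could be affected**
- Upper limit: 125 − 65 = 60 subjects not randomized.
- The share of these who start the run-in is not stated. If it were 25%, 50%, 75% or 100% (assumption), the number would be 0.25 × 60 = 15, 0.50 × 60 = 30, 0.75 × 60 = 45, or 60.
- The limit of 60 is too high, because Protocol 16.3 provides for subjects who fail before the run-in.

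**How many events could be affected**

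Expected events = run-in-only subjects × adverse events per subject × share with no onset date. None of the three factors is in the documents. For illustration only:
- Low: 20 × 0.1 × 0.01 = 0.02.
- High: 60 × 0.3 × 0.05 = 0.9.

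These figures show only that, under such assumptions, less than one event is expected.

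**The case against.** The strongest reply is that the case will hardly ever arise. Protocol 10.1 makes the date of first occurrence a required item for each event. Subjects are asked about events at every visit and call, missing data are queried, and the database is cleaned before analysis. Partly known dates have their own rule. What is left is an event with day, month and year all unknown after those steps, in a subject followed for about two weeks. This stands, and it is why the point is minor. It does not make the rule correct when the case does arise.

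A reader might infer that the event disappears from the report. The documents do not support that. SAP 5.3.1 lists every reported event by subject, and listing 16.2.7.1 would show it. Only the count in the summary tables is missing.

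A reader might also infer that the rule distorts the comparison of P-321 with placebo. The affected subjects received only vehicle, before randomization, and belong to neither arm. For randomized subjects, counting an undated event as emergent is a deliberate cautious convention. It matches how the SAP treats missing severity, missing relationship and missing onset time, and it applies equally to both arms. It is not an error in itself. The one exception is an event with a recorded end date before the first double-masked dose: that event cannot have begun, or worsened, after the dose.

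A further caution concerns the remedy. It would be tempting to use the date on which the event was first reported, but Protocol 10.1 does not list that among the items collected. SAP 3.3.5 mentions the form date only when it says that events with an incomplete end date are "assumed to have ended on or before the day the form was completed", which does not show when an event was first reported. Excluding every event reported before Day 1 would also remove events that pre-dated double-masked dosing and then worsened, which Protocol 10.1 and SAP 3.3.7 count as treatment-emergent.

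**Conclusion.** The gap is real and narrow. Read as written, SAP 5.3.1 and 3.3.7 leave an event with a wholly missing onset date out of every adverse event summary table if the subject took run-in placebo and never received double-masked drug. The event remains in the listing.

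The conclusion rests on the wording of the rule, the two population definitions and the table titles, and needs no assumed rate. Its size does depend on assumptions: at most about 60 subjects are open to it, probably fewer, and the number of events cannot be derived from the documents. No efficacy result and no between-arm safety comparison depends on it. It is a minor point, worth correcting because the correction is cheap.

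**What to change.** In SAP 5.3.1 and 3.3.7, apply the rule for a wholly missing onset date by treatment received:

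- If the subject received double-masked drug, the event is a double-masked treatment-emergent event, unless a recorded end date falls before the first double-masked dose. In that case it is counted in the run-in period.
- If the subject received only run-in placebo, the event is a run-in treatment-emergent event, unless a recorded end date falls before the first run-in dose.
- Events that increase in frequency or severity after double-masked dosing remain double-masked treatment-emergent events under the existing definition.

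The second exception is needed because events are collected from consent, before the first run-in dose at Visit 1. The run-in paragraph of SAP 3.3.7 should carry its own version of the rule, so that the two definitions match.

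The cost is a few sentences in the SAP and one derivation step. The rule uses only dosing status, dosing dates and the resolution date, which Protocol 10.1 already collects where applicable. No change to data collection is needed, and the cautious default stays wherever the timing is unknown.

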5.3.2. Clinical Laboratory Assessments

Clinical laboratory assessments will be performed at Visits 1 and 4 (or Early Termination Visit). Actual values and changes from baseline for clinical laboratory test results will be summarized by study visit and treatment using descriptive statistics. Laboratory values will be displayed in the data listings and those that are outside the normal range will be flagged, along with corresponding normal ranges.

5.3.3. Concomitant Medications

Previous and concomitant medications will be coded using the World Health Organization (WHO)

dictionary version September 2016. Concomitant medications for the placebo run-in period and for the double-masked period will both be summarized by frequency of drug classification and generic drug name by treatment and overall. Previous and concomitant medications will be presented in a data listing.

5.3.4. Other Safety Analyses

Actual values and changes from baseline for BCVA and vital signs will be summarized by treatment and study visit using descriptive statistics. A separate table will be produced for the Runin Population summarizing screening, Day 1, and Change from Screening to Day 1 values.

Biomicroscopy and eye examination data will be summarized separately for each eye by treatment and study visit with descriptive statistics for each area. Areas include lashes, eyelid (erythema), eyelid (edema), conjunctive (erythema), conjunctiva (edema), tear film debris, cornea (endothelial changes), cornea (edema), anterior chamber (cells), anterior chamber (flare), and lens pathology. Shifts from baseline will be presented for each eye, OD and OS.

Drop instillation discomfort will be summarized by treatment and study visit with descriptive statistics.

6. **PROTOCOL DEVIATIONS**

Possible protocol deviations will be identified by the clinical team. These data will be displayed in a data listing and sorted by treatment group and subject.

7. CHANGES IN THE PLANNED ANALYSES

No deviations in the conduct of the study or the planned analysis are anticipated. Should any deviations from the analyses specified in the authorized statistical analysis plan arise, such deviations will be documented in the final clinical study report.

8. REFERENCES

CONFIDENTIAL Page 22 08 August 2017

9. **PROGRAMMING CONVENTIONS**

- Page orientation, margins, and fonts: Summary tables, listings, and figures will appear in landscape orientation. There should be a minimum of a 1.25" boundary on the upper (bound) edge, and a minimum of a 1.0" boundary on the remaining three edges. Output should be printed in Courier New with a point size of 8. Titles may be printed using a larger font (e.g., Arial point size 10).
- Identification of analysis population: Every summary table and figure should clearly specify the analysis population being summarized. Listings will be prepared for all subjects.
- Group headers: In the summary tables, the group headers will identify the summary group and the sample size for the indicated analysis population. Of note, the header's sample size does not necessarily equal the number of subjects actually summarized within any given summary module; some subjects in the analysis population may have missing values and thus may not be summarized.
- Suppression of percentages corresponding to null categories: When count data are presented as category frequencies and corresponding percentages, the percent should be suppressed when the count is zero in order to draw attention to the non-zero counts.
- Presentation of sample sizes: Summary modules should indicate, in one way or another, the number of subjects actually contributing to the summary statistics presented in any given summary module. As mentioned above, this may be less than the number of subjects in the analysis population due to missing data.
 - In the quantitative modules describing continuous variables (and thus presenting sample size, means, and standard deviations), the sample size should be the number of non-missing observations. The number of missing observations, if any, will be noted.
 - For categorical variables that are presented in frequency tables, the module should present the total count in addition to the count in each category. Percentages should be calculated using this total as the denominator, and the percentage corresponding to the sum itself (that is, 100%) should be presented so as to indicate clearly to a reviewer the method of calculation. The number of missing observations, if any, will be noted.
- Sorting: Listings will be sorted by treatment group, subject number and date, if applicable. If a listing is sorted in a different manner, a footnote will indicate as such.
- General formatting rules: Rounding for all variables will occur only as the last step, immediately prior to presentation in listings, tables, and figures. No intermediate rounding will be performed on derived variables. The standard rounding practice of rounding numbers ending in 0-4 down and numbers ending in 5-9 up will be employed.

CONFIDENTIAL Page 23 08 August 2017

- The presentation of numerical values will adhere to the following guidelines:
 - Raw measurements will be reported to the number of significant digits as captured electronically or on the CRFs.
 - Standard deviations will be reported to one decimal place beyond the number of decimal places the original parameter is presented.
 - Means will be reported to the same number of significant digits as the parameter.
 - Calculated percentages will be reported with no decimals.
- Dates will be formatted as DDMMMYYYY. Partial dates will be presented on data listings as recorded on CRFs.
 - Time will be presented according to the 24-hour clock (HH:MM).

